**3 \* Describe the relevant prior experience and gaps in current knowledge. Describe any relevant preliminary data:**

Coordinated pain self-management planning reduces reliance on opioids: using instead physical activity, mental health strategies, mind-body practices such as Yoga, sleep optimization, medication safety, and improvements in environmental factors such as social supports and home safety. Coordination of care is a time-intensive clinical activity that is highly dependent on practitioner education, experience, and proficiency. This is a novel, scalable solution to a major public health problem impacting Veterans of all ages.

The value of an App for chronic pain self-management was examined in preliminary studies. We gathered preliminary impressions about the experience of potential users, utilizing the prototype App. There was tremendous enthusiasm on the part of clinicians for a solution to promote patient engagement with effective pain self-management activities. One provider said "Wow, this would be really great to have for use with my patients". Providers were excited to learn about the evidence-based studies that have recently reported on effectiveness of pain self-management, Table 4. They were very interested to have a tool that would link patients to evidence-based practices and wanted to be able to use the app themselves to encourage patients in using effective non-pharmacological activities. We've had interest from CLC, primary care, and specialty care providers. Next, we met informally with a group of several Veterans, during a coffee break at the VAMHCS GRECC GeroFit program. These older Veterans navigated the App prototype easily and quickly grasped the concept of putting together a plan. They described it as 'helpful', 'liked the diary/tracker', and liked the colorful interface. Several Veterans wanted to know: "When will the App be available?"

**4 \* Provide the scientific or scholarly background, rationale, and significance of the research and how it will add to existing knowledge:**

Chronic low back pain (cLBP) causes more disability than any other condition worldwide and affects 33% of Veterans impairing functional capacity, quality of life, and mental health, while increasing medication reliance and substance abuse. In Veterans, co-occurrence of chronic pain with mental health and substance use conditions, and opioid treatment increases suicide and inadvertent death. Severe cLBP, defined as interfering greatly with normal activity and present on most or all days, affects 20% of Veterans with cLBP.

Interventions to improve functional outcomes and reduce health burdens are a major priority for VA. Despite cLBP having a profound impact on health, it is not well understood and simple therapies have not worked. One potential key is that cLBP is a form of chronic pain, i.e. pain that persists beyond the period of normal healing. Prevalent in older adult and women Veterans, chronic pain leads to poor mental and physical health, is devastating to cognition and function, and importantly requires informed management.

Conceptual Framework. In the last year, systematic reviews have laid a new foundation for pain self-management. Now, there is a huge unmet need for innovative tools for knowledge transfer to patients and providers: i.e., a roadmap to coordinate evidence-based pain-reducing activities into daily life. The need is acute because as we've shown previously, medical graduates have little or no training in pain and pain self-management. Although single self-management activities, e.g. moderate exercise, may decrease pain slightly, multi-dimensional evidence-based pain self-management has superior outcomes. The goal of comprehensive pain management is connecting patients with personalized coordinated multi-dimensional evidence-based plans for pain self-management (C-MEPPS). Pain self-management usually occurs through collaboration between patient and provider; the patient acquires a tailored, multidimensional evidence-based plan leading to pain consuming less of the patient's life, Figure 1. Positive, health-focused, value-based activities become the focus of attention. In the process, pain becomes a footnote in the patient's life, not gone, but no longer dominant. C-MEPPS can be an important element of successful management of chronic pain including low back pain, headache, and arthritis. By contrast, unstructured self-management shows lower efficacy.

Current status. Right now, creating C-MEPPS requires patient and provider to invest hours of effort to work through the activities appropriate for pain self-management, and to assemble the options in a coordinated manner. One major component is time to discuss how various options impact pain outcomes, another component is discovering what activities appeal to the patient. Creating C-MEPPS in the traditional manner is severely limited by health system constraints, amplified by the absence of training in comprehensive pain management. Although the VA "supports self-management as the foundation for all steps of pain care...", at present, innovative evidence-based tools supporting pain self-management are a major need.

Our solution: A novel, scalable roadmap for pain self-management using peer-reviewed evidence; aligned with values-oriented approaches, like those of the Atlanta VA Empower Veterans Program. Our goals are: a) empowering Veterans to learn about appealing and effective choices for pain self-management, b) supporting Veterans in combining appropriate activities for coordinated pain self-management and c) engaging Veterans in planning change and effective lifestyle management, creating C-MEPPS through use of a mobile App: READY-GO Pain. The App currently exists as a hyperlinked graphical interface but requires further development and pilot testing during the period of this SPIRE proposal. Web-encoding has already started with GRECC seed funds. The App will provide Veterans with brief psychoeducation about chronic pain self-management, evidence-based options for pain control, a concrete Veteran-designed plan, a simple way to track activities, and reports to share with the healthcare team.

## Supporting Literature

1 \* Provide a summary of current literature related to the research: **If you uploaded a separate research protocol document in the 'Research Protocol' page, cite the applicable section and page numbers from that document in the answer box below.**

Low back pain affects 1 in 3 Veterans. Surgery isn't appropriate for most back pain and interventional care has limited impact on long-term outcomes. Robust evidence supports broader use of non-pharmacological therapies such as physical activity, mind-body activities, psychoeducation, and strategies such as pacing and sleep hygiene for chronic pain. Potentially, the most effective approach is referral to a comprehensive pain management program involving an interprofessional team of physicians, nurses, pharmacists, physical therapists, clinical psychologists and others. These programs lead to creation of coordinated multi-dimensional, evidence-based plans for pain self-management (C-MEPPS) tailored to each patient. This approach, while effective, is extremely resource intensive; and access is limited by health system factors.

Because the number of patients with chronic low back pain (cLBP) far outstrips the health system capacity for comprehensive management, novel scalable solutions that increase patient access to effective therapies are of high priority. One approach is to train primary care providers to engage patients in multidimensional evidence-based plans for pain self-management, and to negotiate the development of C-MEPPS in the context of a primary care visit. While hypothetically appealing, the feasibility of multiple 40-minute counseling sessions in primary practice where the typical visit lasts less than 20 minutes and needs to address a full spectrum of medical needs is not tenable. Alternatives are essential. Our program aims to accelerate knowledge transfer and support primary care providers and patients in pain self-management. We will connect patients and providers to the broader spectrum of evidence-based therapies and facilitate positive behavior change.

## Study Procedures

**If you uploaded a separate research protocol document in the 'Research Protocol' page, cite the applicable section and page numbers from that document in the answer boxes below. (If this study is a collaborative UM/VA study please list each procedure that is being conducted and the locations where it is being conducted.)**

1 \* Describe all procedures being performed for research purposes only (these procedures would not be done if individuals were not in the study) and when they are performed, including procedures being performed to monitor subjects for safety or to minimize risks:

Patients will be recruited from multiple clinics and intentionally include older and female Veterans. The study coordinator will recruit and consent Veterans. There are three study groups including focus group, one-on-one interview group, and pilot study group. Veterans will be recruited separately for each of these study groups, necessitating separate consent forms.

Procedures:

Phase 1: Veteran focus group

- Single occasion, focus group discussion: Up to five Veterans, recently graduated from the Empowering Veterans Program at the Baltimore-Loch Raven VA will meet during the first quarter of funding for this program. The group will be introduced to the prototype App on tablet computers. Using open semi-structured interviews, we will explore their use of non-pharmacological pain self-management strategies, with special attention to understanding use of language and how existing strategies link to labels and the values they associate with each. A total of five interface options will be included, to assess appeal, perceived navigability of these options, and input on design features and usability. Brief questionnaires will be completed at the end of the focus group session and compensation for participation will be distributed. (Site: Loch Raven VA)

Phase 2: Veteran Pre-pilot group

- Single one-on-one interview: Using open semi-structured interviews, we will explore their use of non-pharmacological pain self-management strategies, with special attention to understanding use of language and how existing strategies link to labels and the values they associate with each. A total of five interface options will be presented to the interview subjects and rated for appeal, perceived navigability, design features, and usability. Validated questionnaires will be completed, see details below. Compensation for participation will be distributed.
- o Five Veterans from Empowering Veterans Program at the Baltimore-Loch Raven VA; (Site: Loch Raven VA)
- o Five female Veterans from the Women's health clinic; (Sites: Baltimore VAMHCS and Fort Meade VA)

Our pre-pilot objective is to reach two groups of Veterans: 1) 5 Veterans completing the EVP (Empower Veterans Program) and 2) 5 Veterans attending the Women's Health Clinic, in collaboration with [name], Director of Women's Health for VAMHCS. This will provide important feedback for the experience of two different groups: the first group is experienced with non-pharmacological, values-based, approaches to pain management including CBT, ACT, MBSR, and others. The Women's Health Clinic group may not have had formal exposure to non-pharmacological pain management and may require additional information or resources to attain maximal benefit from C-MEPPS. The goal is an App that is useful to the broadest number of Veterans. We will include at least 4 older Veterans among the 10 recruited so the App can be developed with input from older Veterans accessing whole-health integrative approaches to pain self-management.

Phase 3: Veteran Formal pilot testing group

- Multiple visits, phone interviews, and activity monitoring. Once feedback from the pre-pilot group is obtained and further modifications incorporated into READY-GO Pain, the App will be tested with a pilot group.
- 20 Veterans with cLBP a balance of middle-aged and older male and female veterans.
- The study procedures will include:
  - o Recruitment: the study will be introduced to potential study subjects by the PI, study investigators, colleagues, or the study coordinator
  - o Consent: the study will be described in detail to the potential study subjects by PI, study investigators, or the study coordinator. If the study subject agrees to participation, they will be given a pain diary to bring back at the time of the initial visit in 2 weeks time.
  - o Initial visit: the study subject will be introduced to the tablet App and instructed in use, all questions will be answered. The study subject will complete brief questionnaires pertaining to pain, sleep, quality of life, prior App experience, and pain interference. The study subject will be fitted with an actigraph and instructed in the use of the device. A 6-minute walk test will be completed. The Veteran will be given the tablet, loaded with the App, to take home and bring back at the follow-up and final visits.
  - o 1st followup phone call: The study subject will be contact by phone one week after the initial visit. Coaching on App use and troubleshoot of App and actigraph use will be provided. Brief pain and pain interference questionnaires will be administered.
  - o 1st follow up visit: the study subject will be coached regarding the tablet App and actigraph use, all questions will be answered. The study subject will complete brief questionnaires pertaining to pain, sleep, quality of life, prior App experience, and pain interference. The study subject will be fitted with an actigraph and instructed in the use of the device.
  - o 2nd followup phone call: The study subject will be contact by phone 3 weeks after the initial visit. Coaching on App use and troubleshoot of App and actigraph use will be provided. Brief pain and pain interference questionnaires will be administered.
  - o 3rd followup phone call: The study subject will be contact by phone 4 weeks after the initial visit. Coaching on App use and troubleshoot of App and actigraph use will be provided. Brief pain and pain interference questionnaires will be administered.
  - o 4th followup phone call: The study subject will be contact by phone 5 weeks after the initial visit. Coaching on App use and troubleshoot of App and actigraph use will be provided. Brief pain and pain interference questionnaires will be administered.
  - o Final visit, in person 6 weeks after the initial visit: the study subject will be debriefed regarding tablet App, all questions will be answered. The study subject will complete brief questionnaires pertaining to pain, sleep, quality of life, prior App experience, and pain interference. The study subject will be debriefed on use of the Actigraph device. The devices will be collected. A 6-minute walk test will be completed.
  - o Final follow up phone call: The subject will be briefly interviewed two weeks after final visit for final thoughts about the App use experience and any plans to change behaviors as a result of using the App for activity planning.
  - o Veterans from Empowering Veterans Program at the Baltimore-Loch Raven VA; (Site: Loch Raven VA)
  - o Female Veterans from the Women's health clinic; (Sites: Baltimore VAMHCS and Fort Meade VA)

We will examine pilot data on usability, App use, and behavior change, and assess barriers to implementing changes planned by the Veteran through the App (failure mode analysis). The vision is that this will lead to future research on rehabilitation-oriented outcomes such as: functional measures, QoL, and pain.

Importantly, there will be no remote, network transmission of data using the tablet app during this study. Instead, completely de-identified information (i.e. data without any of the 18 HIPAA identifiers) will be entered and stored on the tablet for subsequent download when participants arrive at the VAMHCS facility for their planned in-person visits. Hence, there is no chance that VA sensitive information could be accidentally divulged by using the tablet in the manner detailed for this pilot study.

The data collected from participants with tablet APP is de-identified data. The tablet APP and tablet itself are VA approved so authorized connected to the VA network (WiFi and Wired).

2 \* Describe all procedures already being performed for diagnostic or treatment purposes (if not applicable to the study, enter "N/A"):

N/A

3 \* **Describe the duration of an individual participant's participation in the study:**  
The individual's participation in the study will not exceed 8 weeks.

4 \* **Describe the amount of time it will take to complete the entire study:**  
4 years

5 \* **Describe any additional participant requirements:**

Inclusion criteria include: Veterans receiving care at the VAMHCS, frequent or persistent low back pain (> 3 months), pain  $\geq 3$  on a 0-10 numeric rating scale, willing to participate in trial of non-pharmacological therapies for pain; ability to speak, read, and write as needed for study. Stable treatment.

ID: VIEW4E0280585B400  
Name: V2\_Study Procedures

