## Sample Size and Data Analysis

**If you uploaded a separate research protocol document in the 'Research Protocol' page, cite the applicable section and page numbers from that document in the answer boxes below.**

1 \* Provide the rationale and sample size calculations for the proposed target population:

This study is not powered to find statistically significant differences. Qualitative data interpretation will follow from a priori hypothesis development, in brief: specific design features, e.g. simple design, clear navigation, will improve Veteran experience. Quantitative aspects are not anticipated to attain statistical significance and will be descriptive.

2 \* Provide the plan for data analysis. Include in the description the types of comparisons that are planned (e.g., comparison of means, comparison of proportions, regressions, analysis of variance, etc.), which is the primary comparison/analysis, and how the analyses proposed will relate to the primary purposes of the study:

Both qualitative and quantitative methods of research analysis will be used. Data analysis will be performed utilizing a standard statistical analysis package, SAS and excel will be used to evaluate program development, implementation, qualitative instrument development, complex analytical methods, mixed methods research, and survey methodology.

Qualitatively, the current pilot study is designed to identify common barriers to App use.

Quantitatively, this study will obtain statistical information to guide the development of outcome measures for a Merit-level research proposal to determine the potential effectiveness of this multi-dimensional approach to pain self-management in an App.

ID: VIEW4E02806052800  
Name: v2\_Sample Size and Data Analysis

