## Behavioral Intervention

You indicated that this study involves psychosocial or behavioral interventions.

1 \* **Describe the intervention (duration, number of sessions, focus, etc.):**

Utilization of an Application to assist in care coordination. This will involve daily interaction with the tablet-based App during the 6 week period of the study. The interaction with the App itself could take a few minutes but during planning and education activities could take longer periods such as 30 minutes. The study participants will be coached in using the App. The intention is that the App will assist study participants in planning more healthful activities such as moderate daily exercise and improved sleep habits with an overarching goal of reducing pain intensity and interference.

The pilot phase study participants will meet with study staff multiple times during the study.

Phase 1: Veteran focus group

- Single occasion, focus group discussion: Up to five Veterans, recently graduated from the Empowering Veterans Program at the Baltimore-Loch Raven VA will meet during the first quarter of funding for this program. The group will be introduced to the prototype App on tablet computers. Using open semi-structured interviews, we will explore their use of non-pharmacological pain self-management strategies, with special attention to understanding use of language and how existing strategies link to labels and the values they associate with each. A total of five interface options will be included, to assess appeal, perceived navigability of these options, and input on design features and usability. Brief questionnaires will be completed at the end of the focus group session and compensation for participation will be distributed. (Site: Loch Raven VA). Duration 90 minutes, planning activities with an aim of reducing chronic pain intensity and interference will be discussed.

Phase 2: Veteran Pre-pilot group

- Single one-on-one interview: Using open semi-structured interviews, we will explore their use of non-pharmacological pain self-management strategies, with special attention to understanding use of language and how existing strategies link to labels and the values they associate with each. A total of five interface options will be presented to the interview subjects and rated for appeal, perceived navigability, design features, and usability. Validated questionnaires will be completed, see details below. Compensation for participation will be distributed.

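### Does leaving the viewing order of the five interface options unstated spoil the Phase 2 ratings?

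*Protocol*

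**What the plan says.** Phase 2 is described in the same terms in three places: Justification, Objective, & Research Design (item 2), Study Procedures (item 1) and Behavioral Intervention (item 1). The contact is a "Single one-on-one interview", and "A total of five interface options will be presented to the interview subjects and rated for appeal, perceived navigability, design features, and usability". Participants are five graduates of the Empower Veterans Program and five women from the Women's Health Clinic, and the total is confirmed where the protocol says "We will include at least 4 older Veterans among the 10 recruited".

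On the use of the results, Study Procedures says: "Once feedback from the pre-pilot group is obtained and further modifications incorporated into READY-GO Pain, the App will be tested with a pilot group". Sample Size and Data Analysis gives an expectation for reading the qualitative data, that "specific design features, e.g. simple design, clear navigation, will improve Veteran experience", and adds: "Quantitative aspects are not anticipated to attain statistical significance and will be descriptive".

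None of these sections, nor the Interviews section, states a presentation order, randomisation or counterbalancing. None says whether the options appear one at a time or together.

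**The concern.** Each Veteran rates all five options, so the comparison between options is made within a person. In such a comparison the position of an item can affect its score: raters learn what to look for, tire, or anchor on what they saw first. If all ten Veterans saw the same sequence, each option would occupy only one position. A preference for an option could then not be told apart from a preference for its place in the sequence. Order is set when the interview takes place, so an analysis plan written later could not repair it, and more Veterans under the same sequence would not help.

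What would be at stake is the App taken into the 20-Veteran pilot. If ratings distorted by position steered the modifications, Phase 3 could test a less suitable interface. Phase 2 is also the only step where the protocol says that one person rates several designs, and a balanced order would cost nothing in sample size.

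**Working it through.** **Inputs from the protocol.** Five options, one interview each, and 5 + 5 = 10 Veterans. Across phases, 5 + 10 + 20 = 35 (taking Phase 1 at its maximum of five), which matches the enrolment in Participant Selection. The protocol gives no rating scale, standard deviation, effect size or drift.

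**Step 1: is the confounding real under a common sequence?** Write each rating as Veteran + option + position. That gives 10 × 5 = 50 ratings and 10 + 4 + 4 = 18 parameters.
- Common sequence: the four option columns equal the four position columns, so the rank is 10 + 4 = 14, the same as with no position terms. No option contrast can be separated from position.
- Balanced sequences (a ten-sequence Williams design): the rank is 18 of 18.

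The conditional statement is therefore exact.

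**Step 2: what bias would follow?** Assume a linear drift of d points per position. Between the first and last of five positions the bias is (5 − 1) × d = 4d.

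| Assumed d | Common sequence, first to last | One 5×5 Latin square per group of five |
|---|---|---|
| 0.1 | 0.4 | 0 |
| 0.2 | 0.8 | 0 |
| 0.4 | 1.6 | 0 |

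The last column is zero because every option has mean position (1 + 2 + 3 + 4 + 5)/5 = 3.

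No formal design is needed to remove most of this. If the order simply varied at random between Veterans, a single position would have variance (5² − 1)/12 = 2. An option's mean position over ten Veterans would have standard deviation √(2/10) = 0.45. Times d, that is about 0.04, 0.09 and 0.18 points for the three drifts.

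**Step 3: can this become a risk of choosing the wrong interface?** A simulation with ten raters and one option truly 1 point better gives the chance that this option has the highest mean. With a within-rater standard deviation of 2.0 and d = 0.1 it is 66% under a common sequence against 68% balanced. With a standard deviation of 1.0 and d = 0.4 it is 58% against 96%. The loss thus runs from about 2 to 38 percentage points, depending wholly on inputs that the protocol does not supply. At the upper end the bias of 1.6 points exceeds the assumed true advantage of 1.0. The calculation also presumes that the option with the highest mean is adopted. The protocol has no such rule: feedback leads to modifications, which may combine features from several options. These percentages therefore do not measure a risk in this study.

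**Step 4: does the protocol meet the conditions?** The confounding needs both (a) sequential presentation and (b) one sequence for all ten Veterans. The text states neither. If the options are laid out together, the issue shrinks to layout or the order of rating.

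**The case for a change.** The best argument for a change is that calling the numbers descriptive does not protect them. Position bias moves the means and ranks themselves, not just a p-value, and those summaries inform a real decision about the App. Order is also settled at the interview, so it cannot be deferred to an analysis plan. Ten Veterans in two groups of five fit a balanced scheme exactly, and the cost is an order sheet and one recorded field.

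Most of that is right as far as it goes. The confounding under a common sequence stands, and so does the point that it could not be undone afterwards in the ratings. What does not stand is the step from silence to fault. The protocol does not adopt a common sequence. Details of this kind can reasonably sit in an interviewer's guide. The application lists uploaded scripts and a grant research plan whose contents are not shown. The scripts listed under Interviews appear to be for telephone contact, so they cannot be assumed to settle the matter, but neither can it be assumed that order is unmanaged.

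The ratings also do not stand alone. The one-on-one interviews are open and semi-structured, so a Veteran can explain what works and what does not, and those reasons are less exposed to position than a score. Phase 1 separately gathers views on five interface options. The stated expectation about design features guides qualitative reading and names no contrast between options.

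**Conclusion.** No change to the plan is needed. It is true that the protocol leaves the viewing order open, and that one common sequential order would confound position with interface in the ratings: rank 14 of 18, and a first-to-last bias of four times whatever drift exists. But the plan does not prescribe that order. Followed as written, it produces formative comments and descriptive ratings from ten interviews, with no test and no selection rule for a position effect to overturn.

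The size of any effect is unknown. The biases of 0.4 to 1.6 points rest on assumed drifts of 0.1 to 0.4 points per position, and no percentage-point loss can be attributed to the study. An interviewer who varies the order and notes it closes the gap without an amendment. The conclusion would differ if a study document required the same sequence for everyone and the design were chosen on mean ratings alone; nothing in the protocol says so.
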